--	--

	
The final analysis data from the HERALD study (CV-NCOV-004), conducted with the same study vaccine (CVnCoV) was made available on the 30th June 2021. The HERALD study results were statistically significant for the primary study objective. The final efficacy analysis showed an overall efficacy of 48.2% (LL (lower limit) 31,0%) for CVnCoV in the prevention of COVID-19 cases of any severity, reaching the predefined success criterion. Similar confirmatory results were observed in the prevention of moderate to severe COVID-19 cases, a key secondary efficacy objective, with an overall vaccine efficacy of 70.7% (LL 42.5%).
 
Whereas, in the HERALD study, CVnCoV efficacy in the prevention of COVID-19 cases of any severity was confirmed in the 18 to 60 age group (VE 52.5%, LL 36.2%), data in study participants older than 60 years was not conclusive including due to the low number of cases (only 9% of all cases) and low number of participants under follow up in that age group. There was also no clear trend of efficacy in this age group. Similarly, vaccine efficacy in the prevention of moderate to severe disease was 77.2% (LL 51.8%) in participants 18 to 60 years old and no conclusive results were observed in participants older than 60 years.
 
Since the efficacy results from the HERALD study for CVnCoV are available and all subjects in the CV-NCOV-005 study are currently eligible to receive an authorized vaccine, all subjects in this CV-NCOV-005 study will be unblinded.
 
Each subject will be informed by the study physician of the available study results and whether he/she received the study vaccine (CVnCoV) or placebo in the study. The purpose of this measure is to provide the participants/subjects with sufficient information so that they can decide whether to take an authorized vaccine or not in a fully informed way.
 
All subjects that received placebo in this study should follow the official recommendations regarding vaccination against SARS-CoV-2 outside of the study; no further follow up will be required and the subjects will leave the study.
 
The subjects that received at least one dose of CVnCoV and already decided to take an authorized vaccine, will be asked to remain in the study to allow safety follow-up:
 
Since for subjects older than 60 years, a favorable benefit-risk for CVnCoV could not be established based on the HERALD study results, subjects who received CVnCoV should follow the official recommendations regarding vaccination against SARS-CoV-2 outside of the study.
 
Subjects 60 and younger willing to take the authorized vaccine should inform the site and are encouraged to speak with the study doctor/ investigator for further information on the CVnCoV final efficacy analysis results and how to access the authorized vaccine, out of the clinical study setting.
 
All subjects receiving the authorized vaccine following at least one dose of CVnCoV should continue the safety follow-up in the study until the end of the trial (Schedule of Activities- Table 2).
 
To date, no clinical trial has proactively investigated or been designed to evaluate the administration of authorized vaccines after vaccination with CVnCoV.
 
A post-hoc analysis in June 2021 showed that 438 participants across CVnCoV studies were administered authorised COVID-19 vaccine through national vaccination programmes after having received one or two 12µg-doses of CVnCoV during clinical studies. The most frequent authorised

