### **7.3.1 Randomization**

Approximately 2,520 subjects 18 years of age or older will be enrolled at the site at Mainz University, Germany and will be randomized in a 1:1:1 ratio (840 by randomization group) to receive either 1 of 2 different lots of CVnCoV (CVn CoV Lot 1 group and CVnCoV Lot 2 group) or placebo (placebo group). The randomization will be performed centrally and stratified by age group (18 to 60 and  $\geq 61$  years of age). The randomization scheme will be generated and maintained by the Statistical and Data Management group at the contract research organization (CRO), PRA. Subjects will be enrolled into the trial online and randomized using an interactive web response system (IWRS). After demographic and eligibility criteria are entered into the system, subjects enrolled into the trial will be assigned their treatment assignment.

The first 1,260 subjects enrolled are planned to be included in the Immunogenicity/Reactogenicity Subset.

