### ***Sensitivity Analysis***

As a sensitivity analysis, the time to first-occurrence of virologically-confirmed COVID-19 cases (according to the case definition) may be analyzed.

The Kaplan-Meier curves will display the estimated probabilities of not developing COVID-19 and log-rank test will be performed.

The time to first-occurrence of virologically-confirmed COVID-19 (date of symptoms onset) will start 15 days after the second vaccination.

Subjects who do not develop COVID-19 will be censored at the date of trial termination or cut-off date for analysis whichever comes first.

An additional sensitivity analysis may include a Cox proportional hazards regression model adjusted for relevant baseline covariates specified in the SAP.

More details on the analysis methods will be described in the SAP.

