8.6 Randomization and Blinding

The trial is randomized, observer-blinded, and placebo-controlled. The difference in appearance of the investigational CVnCoV vaccine and placebo requires the trial to be conducted in an observer-blinded manner.

The pharmacist/personnel preparing the trial vaccine at the site is not blinded to the identity of the trial vaccine being administered to the subject. However, the vaccinator, investigator and all site personnel involved in the conduct of the trial are blinded to trial vaccine and subject treatment assignments. To maintain the blinding of the vaccinator, the unblinded pharmacist/site personnel provide the dose of trial vaccine to the vaccinator pre-filled in a syringe with a label covering the liquid contents so that it is not visible. All personnel at PRA/ICON and Sponsor directly involved in the conduct of the trial is also blinded. There are certain individuals at PRA/ICON and Sponsor whose function requires them to be unblinded during the trial (e.g., unblinded monitoring for trial vaccine accountability in the pharmacy; unblinded independent statistician assisting the DSMB; review of immunogenicity data). These unblinded individuals are identified and their responsibilities documented.

As the immunogenicity results would unblind the subject's treatment assignment, an independent laboratory performing the assays keep the results in strict confidence. An unblinded person, named at the start of the trial and independent of the conduct of the trial, has the responsibility of reviewing the quality of the immunogenicity data as it is being generated. This person maintains the results in strict confidence. To maintain the blind, the immunogenicity data is only merged with the clinical database at CDISC level following unblinding of the trial.

The first immunogenicity analysis is scheduled for August 2021. PRA/ICON who is to perform this analysis is unblinded on that occasion.

Approximately 2,520 subjects 18 years of age or older are enrolled at the site at Mainz University, Germany and are randomized in a 1:1:1 ratio (840 per randomization group) to receive either one of two different lots of a 2-dose schedule of CVnCoV or placebo. The randomization is performed centrally and stratified by age group (18 to 60 and ≥ 61 years of age).

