12.0 Statistical Methods

Unless otherwise noted, categorical variables are summarized using counts and percentages. Percentages are presented with one decimal place, except 100% is displayed without any decimal places and percentages are not displayed for zero counts. Continuous variables are summarized using the number of observations (n), mean, median, SD, 1st Quartile (Q1), and 3rd Quartile (Q3), minimum and maximum values. Mean, median, Q1 and Q3 are presented to 1 decimal more than original data. SD is presented with 2 decimals more than original data. Minimum and maximum match the decimal points in the original data. The maximum number of decimals is 4, unless otherwise stated.

In general, all data summaries are presented overall and by vaccine group. Thereby, the CVnCoV data is presented for pooled CVnCoV lots and split by lot. Efficacy outputs are not split by lot and do not have an overall column presented. Selected outputs are **additionally** presented using further subsetting of the data. This is specified explicitly in the respective sections.

If not stated otherwise, p-values from statistical tests are two-sided and CIs are calculated using a 95% confidence level.

Age group is used as a factor for stratification of randomization. The efficacy analyses are in general **not** adjusted for this factor.

No imputation of missing data other than that described in Section 10.3 is performed.

All data collected during this trial is displayed in data listings, unless otherwise specified. Screening failures are excluded from all listings and tables if not otherwise stated. Listings include all relevant assigned/derived variables. If not explicitly stated, listings do not show imputed data, but present data as reported.

All data summaries and tabulations are prepared using SAS® Version 9.4 or higher.

In agreement with the sponsor it was decided to not perform some of the analyses in the EOT analysis. Therefore some of the below analyses were never performed. For details, please refer to Appendix 4

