12.8.1 Secondary Efficacy Endpoint Analysis

12.8.1.1 First Episodes of Covid-19 Cases

Occurrence of first episodes of virologically-confirmed (RT-PCR positive) cases of COVID-19 of any severity meeting the case definition for the efficacy analysis is analyzed as follows:

From the number of occurrences of respective cases (COVID-19 cases or seroconversion) in each vaccine group, the VE corresponding to each endpoint is calculated as follows:

$$VE = 1 - \frac{p}{1-p} * \frac{1}{r}$$

Thereby, p denotes the proportion of cases coming from the pooled CVnCoV group among all cases and r is the ratio of total follow-up time of subjects in the pooled CVnCoV group over the total follow-up time of subjects in the placebo group (see Section 10.11).

An exact two-sided 95% Pearson-Clopper CI for p is calculated. From this, the Lower Limit (LL) and Upper Limit (UL) of the 95% CI for the VE is calculated from the UL and LL of the CI for p as:

$$LL_{VE} = 1 - \frac{UL_p}{(1 - UL_p) * r}; UL_{VE} = 1 - \frac{LL_p}{(1 - LL_p) * r}$$

The following is presented for the analysis of these secondary efficacy endpoints:

- Number and percentage of subjects with a respective case (COVID-19 case or seroconversion)
- Total follow-up time (years) in each vaccine group,
- Calculated proportion of cases coming from the pooled CVnCoV group among all cases (p),
- Ratio of total follow-up time of subjects in the pooled CVnCoV group over the total follow-up time of subjects in the placebo group (r),
- Estimated VE based on p and r,
- 95% CIs for p and VE

This secondary efficacy analysis is performed on the EAS.

For any analysis requiring the serostatus at baseline or Visit Day 43 the information of the adjudication of COVID-19 cases is used, if available (Section 10.7.5). Otherwise the information of the N protein blood samples taken at baseline and Visit Day 43 is used (Section 10.6.1).

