12.8.1.4 Sensitivity Analyses

As a sensitivity analysis, the time to first occurrence of virologically-confirmed COVID-19 case of any severity according to the efficacy case definition is analyzed. Calculation of the time to first occurrence and censoring rules is applied according to Section 10.11.

KM estimates for the probability of not developing COVID-19 (hereafter referred to as “survival”) are computed for each vaccine group (pooled CVnCoV and Placebo). Estimates for Q1, median and Q3 of the survival times are presented. Log rank test comparing the vaccine groups is performed. The summaries are provided by vaccine group.

A Cox Proportional Hazard model is used to model the time to first occurrence of virologically-confirmed COVID-19 cases according to the efficacy case definition. The model includes the vaccine group (pooled CVnCoV or Placebo) as a factor and is adjusted for the stratification factor age at baseline (18 to 60 and ≥ 61 years). The estimated Hazard Ratios for the CVnCoV vaccine group versus placebo and corresponding 95% CI is presented. The CIs are derived based on the Wald test.

These sensitivity analyses are performed on the EAS.

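### Reported VE pools over age although randomisation was stratified by age; an age-stratified VE is a nearly free addition, and the status of the only age-adjusted analysis is unclear

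*SAP*

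**What the plan says.** On allocation, SAP 8.6 states "The randomization is performed centrally and stratified by age group", with groups 18 to 60 and 61 or older. Under Protocol 7.3.1 subjects "will be randomized in a 1:1:1 ratio (840 by randomization group"), which is 2:1 for pooled CVnCoV against placebo.

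On analysis, SAP 12.0 says "Age group is used as a factor for stratification of randomization. The efficacy analyses are in general" and the sentence ends by saying they are not adjusted for this factor. SAP 12.8.1.1 defines VE as 1 - [p/(1-p)] × (1/r), where "p denotes the proportion of cases coming from the pooled CVnCoV group among all cases and r is the ratio of total follow-up time", pooled over age. The exact interval for VE is the Clopper-Pearson interval for p, transformed with the same r. Protocol 10.3.7.1 gives the same formula.

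On adjustment, Protocol 10.3.7.1 offers one option: "An additional sensitivity analysis may include a Cox proportional hazards regression model adjusted for relevant baseline covariates specified in the SAP". SAP 12.8.1.4 takes it up with a Cox model on the Efficacy Analysis Set (EAS) that "is adjusted for the stratification factor age at baseline" and gives a hazard ratio with a Wald interval. SAP 6.1 item 17 then says the Kaplan-Meier sensitivity analysis of this endpoint is not done, although 12.8.1.4 still describes Kaplan-Meier estimates and a log-rank test. Item 17 does not name the Cox model. SAP 12.0 adds that some described analyses were never run and refers to Appendix 4, which is kept outside the SAP.

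**The concern.** Stratifying randomisation by a factor and then ignoring it in the analysis forgoes an adjustment that is already paid for. Stratified allocation also fixes headcounts only; it does not fix the person-time that enters r.

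The EAS is formed after randomisation and drops subjects who were unblinded or received an authorised vaccine before 15 days after dose 2 (SAP 9.5.5). Follow-up then stops the day after unblinding or authorised vaccine, whichever is earlier (SAP 10.10). Subjects could ask to be unblinded, and some may have taken an authorised vaccine without unblinding. The Protocol synopsis says such vaccines went first to defined risk groups and were open to all adults from 7 June 2021. If these processes differed by arm within an age group, r would differ between age groups. If incidence also differed by age, the pooled VE would carry some confounding by age.

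No output described in the SAP would let a reader check this. SAP 12.1 summarises censored subjects by whether it happened before or after dose 2, not by age, and SAP 12.8 has no table of cases or person-time by age group.

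**Working it through.** The plan states no expected number of cases, precision or power for efficacy, so there is no efficacy figure to reproduce. The check compares the SAP formula with an age-stratified estimate on expected counts.

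**Inputs from the documents**
- Allocation 2:1 pooled vaccine to placebo within each age stratum (1,680 / 840 = 2).
- VE of 48.2%, the sister trial's overall result in the Protocol synopsis, used for illustration as the common true VE.

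**Assumed inputs (not in the documents)**
- w, the share of placebo person-time in subjects 61 or older: 5% to 20%.
- IRR, incidence in older relative to younger subjects: 0.3 to 2.
- Person-time ratios r_y (younger) and r_o (older): between 2 and 4.

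**Formula.** Set placebo person-time to 1 and younger placebo incidence to 1.
- Placebo cases: (1-w) + IRR·w
- Vaccine cases: (1-VE)·[r_y(1-w) + IRR·r_o·w]
- Pooled r: r_y(1-w) + r_o·w
- Crude VE: 1 - (vaccine cases / placebo cases) / r

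The crude rate ratio equals (1-VE) multiplied by a factor. The numerator of that factor exceeds its denominator by w(1-w)(r_o - r_y)(IRR - 1). The difference is zero if r is the same in both strata or if incidence is the same in both strata. Both must differ for any bias to arise.

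**Worked case.** w = 10%, r_y = 2, r_o = 3, IRR = 2. Placebo cases 0.9 + 0.2 = 1.1. Vaccine cases 0.518 × (1.8 + 0.6) = 1.243. Pooled r = 1.8 + 0.3 = 2.1. Crude VE = 1 - 1.243/1.1/2.1 = 46.2%.

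**Crude VE (%) when the true VE is 48.2% in both strata**

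| w | r_y / r_o | IRR 0.3 | IRR 0.5 | IRR 1 | IRR 2 |
|---|---|---|---|---|---|
| 10% | 2 / 2 | 48.2 | 48.2 | 48.2 | 48.2 |
| 10% | 2 / 2.5 | 49.1 | 48.8 | 48.2 | 47.2 |
| 10% | 2 / 3 | 49.9 | 49.4 | 48.2 | 46.2 |
| 10% | 3 / 2 | 47.0 | 47.4 | 48.2 | 49.7 |
| 20% | 2 / 4 | 53.8 | 52.0 | 48.2 | 42.4 |

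The Mantel-Haenszel age-stratified VE is 48.2% in every row. The moderate rows (r of 2 against 2.5 or 3, 10% older) give errors of -2.0 to +1.7 points. The extreme row gives -5.8 to +5.6.

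**Sampling error for scale.** Exact 95% interval from the SAP 12.8.1.1 method with r = 2:

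| Total cases (vaccine) | VE | 95% CI |
|---|---|---|
| 10 (5) | 50.0% | -117.3% to 88.5% |
| 20 (10) | 50.0% | -33.9% to 81.3% |
| 40 (20) | 50.0% | 2.1% to 74.5% |
| 80 (41) | 47.4% | 16.3% to 66.9% |

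Even with 80 cases the interval spans about 51 points, against a worst-case error of about 6.

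**The case against.** The strongest reply is that no bias is shown. Allocation is 2:1 within strata, and both arms are censored by the same rule the day after unblinding or authorised vaccine. Person-time therefore ends before a subject can act on a revealed allocation. If older subjects leave earlier, both arms shrink and r stays near 2. A gap in r needs a difference by arm within age, for example subjects guessing their allocation from reactogenicity, and the documents report none. This stands, and it is why the point is minor.

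It is also said that age adjustment is already planned. That stands only in part. The Cox model is a sensitivity hazard ratio with a Wald interval; it does not adjust the reported VE or its exact interval, and the SAP does not make clear whether it is run. SAP 10.7.5 mentions an analysis of cases by age group, but section 12.8 describes none.

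Efficacy is also secondary and descriptive, without success criteria (Protocol 10.3.7.1), so no decision turns on a point or two of VE. That also stands.

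Two stronger readings are tempting and are not supported:
- A reader might infer that efficacy is known to differ by age. The Protocol synopsis says only that sister-trial "data in study participants older than 60 years was not conclusive", partly because of few cases (9% of the total) and few participants under follow-up. That is lack of information, not evidence of a different VE.
- A reader might pair 52.5% at 18 to 60 with an assumed 0% above 60 and note that crude VE would then fall between 35% and 51%, depending on age mix. That calculation uses r = 2 in both strata. With equal r the vaccine share of cases under a common VE is the same in each stratum, so a stratified common-VE model returns exactly the crude estimate. The range illustrates effect modification, not confounding that stratification would remove.

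**Conclusion.** The point holds as a low-cost improvement. The reported VE and its exact interval ignore the randomisation stratum, and the one age-adjusted analysis has unclear status. If the Cox model was dropped along with the Kaplan-Meier analysis, no age-adjusted efficacy estimate remains.

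The documents do not show that crude VE is biased. Bias needs arm-related EAS exclusion or censoring within age together with a difference in incidence by age. Under assumed moderate inputs the error is about 0 to 2 points, and about 6 at the extreme, which is small beside the confidence interval. The age share, incidence ratio and stratum-specific r behind these figures are assumptions; the documents give none of them for this trial. Reporting by stratum would replace them with data.

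**What to change.** 1. In SAP 12.8.1.1, add a VE and 95% CI stratified by the randomised age group, either exact conditional or from a Poisson model with stratum terms and a log person-time offset. Keep the crude VE as specified. SAP 6.0 says version 4.0 was written by an unblinded team, so label the stratified estimate supportive.
2. Tabulate cases, person-time and r by arm and age stratum on the EAS. If the two r values are close, the table settles the matter.
3. Reconcile SAP 6.1 item 17 with 12.8.1.4, and state whether the Cox model and the log-rank test are run.
4. Name one source for age group. SAP 10.7.5 uses CRF age for cases by age group, while 10.12 uses the age recorded in the IWRS.

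The cost is a few lines of SAP text, one procedure call and one table. The age group is already defined, and no new data are needed.

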12.1 Subject Disposition

The number and percentage of subjects who prematurely withdraw from treatment, prematurely withdraw from the trial and a breakdown of the corresponding reasons for treatment withdrawal and early trial discontinuation is provided. Reasons for withdrawal are listed for subjects who prematurely withdraw from treatment or prematurely withdraw from the trial.

The number and percentage of subjects randomized and treated is presented with the number and percentage of subjects included in each analysis set. Reasons for exclusion from each analysis set are not tabulated, but are listed.

Subjects whose data is censored due to unblinding for AV treatment being available, are summarized for unblinding and / or AV use before dose 2 and after dose 2 for SAS and randomized subjects. A separate listing is provided indicating the date a subject was unblinded / received an AV. Subjects who have received an AV without being unblinded are also included in that listing.

The number and percentage of subjects who were not stratified correctly is presented along with the number of subjects who received an incorrect vaccine at first and/or second vaccination. The summary is done for all randomized subjects. Subjects are also listed accordingly.

12.2 Demographic and Baseline Characteristics

The following demographic data collected at baseline is summarized for the SAS (and PPI at the Immunology IA):

- Age at first informed consent (years),
- Age group (18 to 60 years / \geq 61 years),
- Gender (Female / Male / Undifferentiated / Unknown),
- Ethnicity (Hispanic or Latino / Not Hispanic or Latino / Not Reported / Unknown),
- Race (American Indian or Alaska Native / Asian Indian/ Black or African American / Chinese / Filipino / Japanese / Korean / Native Hawaiian or Pacific Islander / Vietnamese / White / Other / Not reported / Unknown),
- Baseline and Visit Day 43 serology status (Seronegative / Seropositive), see Section 10.6.1 for details.

-
- Baseline and Visit Day 43 serology status, overruled by independent committee adjudication if available (Seronegative / Seropositive), see Section 10.7.5 for details.
 - Height (cm),
 - Weight (kg),
 - Body Mass Index (kg/m²).

12.3 Medical and Surgical History

Medical/surgical history is coded using the MedDRA Version 23.1 or higher. Medical/surgical history is listed for the SAS.

The number and percentage of subjects with any co-morbidity and a breakdown of the corresponding co-morbidities are provided for the SAS.

